Arterial Stiffness	Aortic pulse-wave velocity (PWV), commonly measured as carotid to femoral PWV (cfPWV), is considered to be the gold standard method of assessing arterial stiffness in humans. cfPWV will be measured using the SphygmoCor XCEL system (AtCor Medical, New South Wales, Australia). Briefly, cfPWV will be determined by recording pressure pulse waves at the carotid and femoral arteries using a high-fidelity micromanometer (Millar Instruments, Houston, TX) and calculating the distance between the recording sites divided by the time delay between the carotid and the femoral pulse waves [13].

6.10 Sample size justification. This pilot study will help generate precise estimates of effect variance in the population in which a subsequent larger-scale study will be conducted. Published recommendations for the design of pilot studies indicate that a sample of 18 participants per randomized arm is typically sufficient to estimate a parameter for a future trial [14-16]. The enrollment sample of 54 (n=18 x 3 arms) participants is intended to provide preliminary data necessary to indicate feasibility of a larger trial and to provide descriptive estimates of effects. Based on our experience from the past and current clinical trials conducted at our institute, we do not expect an attrition higher than 15%, therefore, we increased a group size to n=18, which will give us sufficient sample sizes for the pilot purposes after drop-out (n=15 x 3 groups). The data will also provide for nominal estimation (using a 95% CI) of mean changes in dependent variables within each arm. By assuming the mean decrease in SBP after a 6-week of intervention to be 20 mmHg, 10 mmHg and 15 mmHg in the three groups of NREx, PLEx and NR, respectively, and the standard deviation of the SBP decreases to be 10 [16], the sample size of 15 participants for each group can guarantee a power of 85% to detect the difference between the NREx and PLEx groups and a power of about 80% to detect the differences among the three groups. We expect that the differences of the arterial-stiffness measurements among the three groups are larger than those of SBP. Thus, the power numbers for that measure will be larger as well.

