10. Statistical Analysis Plan

The primary analysis will follow an “intent-to-treat” model. Because repeated measures are obtained on individual participants and they are potentially correlated, a mixed-effect linear regression model will be used. Differences in outcome measures at the 3-week follow-up (or 6-week close-out) from baseline for each individual participant will be used as responses, and two dummy variables representing the three treatment groups, age, and gender, and other baseline characteristics of participants will be used as covariates. A random-effect term will also be included in the model to accommodate within-subject data correlation. This analysis will be performed for each outcome variable. The relatively small sample size may imbalance pre-randomization covariates. Thus, caution will be taken in the interpretation of hypothesis testing results.

Literature cited

6. de Picciotto NE, Gano LB, Johnson LC, Martens CR, Sindler AL, Mills KF, et al. *Nicotinamide mononucleotide supplementation reverses vascular dysfunction and oxidative stress with aging in mice*. Aging Cell, 2016. **15**(3): p. 522-30.

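### Section 10 models the 3- and 6-week SBP changes with no visit term and no primary visit, so on its most natural reading it does not estimate the 6-week effect planned in section 6.10

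*Combined protocol and SAP*

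**What the plan says.** Section 10 is the whole analysis plan. It motivates the model thus: "Because repeated measures are obtained on individual participants and they are potentially correlated, a mixed-effect linear regression model will be used". The response is "Differences in outcome measures at the 3-week follow-up (or 6-week close-out) from baseline for each individual participant will be used as responses". On the right-hand side, "two dummy variables representing the three treatment groups, age, and gender, and other baseline characteristics of participants will be used as covariates", and then "A random-effect term will also be included in the model to accommodate within-subject data correlation". The same model serves every endpoint: "This analysis will be performed for each outcome variable". No visit term, treatment-by-visit term or primary visit is given.

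Aim 1 (section 5) is to obtain data for sizing a full-scale trial, with change in SBP as the primary outcome. It gives no time point. SBP is measured at baseline, 3 weeks and 6 weeks, so each participant yields two changes. Pulse-wave velocity (PWV) is measured at baseline and 6 weeks only, so it yields one.

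The only SBP effect in the documents is in section 6.10 and is for 6 weeks: "By assuming the mean decrease in SBP after a 6-week of intervention to be 20 mmHg, 10 mmHg and 15 mmHg" in NREx, PLEx and NR respectively, with an SD of 10 and 15 evaluable participants per arm. That section rests the sample size first on pilot guidance: "a sample of 18 participants per randomized arm is typically sufficient to estimate a parameter for a future trial".

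**The concern.** The repeated-measures rationale and the within-subject random effect point to one model containing both changes. With no visit term, such a model has a single treatment coefficient per contrast, and that coefficient blends the two visits. It is not the 6-week difference on which section 6.10 plans. The model also has nowhere to put a common shift between week 3 and week 6 except residual variation, and if the arms miss visits unequally, part of that shift leaks into the treatment contrast.

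The word *or* in the response definition also allows a less natural reading, with a separate fit at each visit. The week-6 fit would then match section 6.10. But neither visit is ranked first, and with one observation per person the random effect cannot be separated from residual error. The random effect fails in the same way for PWV under either reading, although the PWV treatment contrast stays unbiased.

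What is at stake is mainly Aim 1. Neither the aim nor section 10 says which visit's effect and SD feed the full-scale projection.

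**Working it through.** **Inputs from section 6.10.** NREx minus PLEx at week 6 = 20 − 10 = 10 mmHg; SD 10; 15 evaluable of 18 per arm.

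**Assumed, because the documents give no value.** SD 10 at week 3 too; correlation r between the two changes of 0.5 to 0.7 (0.3 to 0.7 for missed visits); week-3 effect = f × the week-6 effect, with f = 0.5, 0.75 or 1.

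**1. The plan's own figure.** SE = 10 × √(2/15) = 3.65 mmHg and noncentrality = 10/3.65 = 2.74, on 28 degrees of freedom. Power is 84.8% at one-sided 0.05, which reproduces the stated 85%, and 75.3% at two-sided 0.05. Section 6.10 states no alpha or sidedness. The stated power is thus for a simple week-6 comparison.

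**2. What the stated model estimates.** With complete data the coefficient is 10(1 + f)/2, which is 7.5, 8.75 or 10 mmHg for f = 0.5, 0.75 or 1. The SD of a person's mean change is 10 × √((1 + r)/2), which is 8.66 at r = 0.5 and 9.22 at r = 0.7.

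**3. Aim 1 projection if fed from this model** (t-based, 90% power, two-sided 0.05):

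| Source | Effect (mmHg) | SD | n per arm |
|---|---|---|---|
| Week 6 | 10 | 10 | 23 |
| Average, f = 0.5 | 7.5 | 8.66–9.22 | 30–33 |
| Average, f = 0.75 | 8.75 | 8.66–9.22 | 22–25 |
| Average, f = 1 | 10 | 8.66–9.22 | 17–19 |

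For the pilot itself at 15 per arm (two-sided 0.05), power for the average is 58–63%, 71–76% and 82–86% for the three values of f, against 75% for week 6.

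**4. Missed visits.** With n2 participants complete and n1 seen at week 3 only, the random-intercept arm mean is [n2 × (2/(1+r)) × (m3+m6)/2 + n1 × m3] / [n2 × 2/(1+r) + n1], where m3 and m6 are the mean falls. Take f = 0.5, so falls of 10 then 20 in NREx and 5 then 10 in PLEx, with r from 0.3 to 0.7:
- complete data: 7.5 mmHg
- 3 of 18 miss week 6 in both arms: 7.1–7.2
- 3 of 18 in NREx only: 6.8–6.9
- 3 of 18 in PLEx only: 7.8–7.9

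Now suppose no treatment difference, with both arms falling 5 then 10 and 3 of 18 missing week 6 in NREx only. At r = 0.5 the NREx mean is (20 × 7.5 + 3 × 5)/23 = 7.17, where 20 = 15 × 2/1.5. PLEx is 7.5, so the contrast is −0.33. Over r = 0.3 to 0.7 it is −0.29 to −0.36 mmHg.

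**5. Variance components.** With f = 0.5 in every arm, the falls between visits are 10, 5 and 7.5 mmHg. Half of each, squared and averaged, is (25 + 6.25 + 14.06)/3 = 15.1. Without a visit term this is added to the variance and taken from the covariance. The SD becomes √115.1 = 10.7 instead of 10. The correlation becomes (50 − 15.1)/115.1 = 0.30 instead of 0.5, or (70 − 15.1)/115.1 = 0.48 instead of 0.7.

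**6. Scale against pilot precision.** At 15 per arm the 95% half-width of the week-6 contrast is 2.048 × 3.65 = 7.5 mmHg. An estimate of 10 is then compatible with about 2.5 to 17.5 mmHg, or from 332 down to 8 per arm at 90% power.

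**The case against.** Section 6.10 already points to week 6: its effect, SD and power are all for the 6-week decrease, and follow-up ends there. That stands as a signal of intent, but it is a planning assumption that section 10 does not carry into the model.

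The parenthetical *or* may simply mean whichever follow-up an outcome has, since PWV has only one. That is fair, and it is why the per-visit reading is the weaker one. It leaves the pooled model, and its averaging, as the reading to answer.

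The documents do not say that Aim 1 takes its inputs from the section 10 model. Section 6.10 separately promises descriptive estimates and within-arm mean changes with 95% CIs, and a projection could use those. This stands, so the consequence for Aim 1 is conditional. The distorted SD and correlation likewise matter only if the model's variance components are used.

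The study is a pilot, and section 10 itself urges caution with hypothesis tests. That lowers the stakes, but caution over p-values does not define which effect is estimated.

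A reader might go further and infer that pooling costs power or undersizes the next trial. The documents do not support that: they give no week-3 effect, at 75% of the effect by week 3 almost nothing changes, and at 100% the average is the more powerful. Nor should the 75% week-6 figure set beside the stated 85% be blamed on the model; that gap comes from sidedness.

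**Conclusion.** The analysis is wrong as written, with severity between minor and should-fix. Following section 10 on its most natural reading gives a two-visit average of the SBP effect, not the 6-week difference of section 6.10, and specifies a random effect that cannot be identified for PWV.

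The numerical consequence for Aim 1 is a projected 17 to 33 per arm across the scenarios, against 23 from week 6. It arises only if Aim 1 uses this model, and it rests on the assumed week-3 effect, equal SDs and correlation. Its direction is unknown and it is small beside the pilot's sampling error. The bias from unequal missed visits is about 0.3–0.4 mmHg, roughly a tenth of the 3.65 mmHg SE, and needs all the missed week-6 visits to fall in one arm. The case for changing the plan is that the estimate is undefined and the remedy nearly free, rather than that a large error has been shown.

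**What to change.** In section 10:
- Name NREx minus PLEx at week 6, with its 95% CI, as the primary SBP estimate.
- Add visit, treatment-by-visit and baseline SBP to the repeated-measures model.
- State that the Aim 1 effect and SD come from week 6, and keep the two-visit average as a secondary estimate.
- For PWV and other outcomes with one follow-up, use ANCOVA on the baseline value with no random effect.
- State which SBP summary is primary. The opening summary and sections 4 and 5 speak of daytime SBP, while section 6.9 lists 24-h BP with overnight readings; these need reconciling.

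The covariance structure and degrees-of-freedom method can be left to the trial statistician.

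The cost is wording and a few model terms, with no new visits, data or participants. The one statistical price is precision: if the effect is nearly complete by week 3, the week-6 contrast has an SE of 3.65 mmHg against 3.16–3.37 for the average (8.66 or 9.22 × √(2/15)) at 15 per arm. That is the reason to keep the average as secondary.

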6.3 Screening and Study Entry: Participants deemed eligible based on an initial phone screening by our front desk manager, will be encouraged to consult with their physician and invited to an in-person screening visit. During this visit, potential participants will first be asked to give their informed consent and then will be screened for study entry criteria. Initial screening procedures will include a review of their medical history, medication use, a physical exam or nursing assessment, physical activity levels, cognitive function (assessed by the Mini-Mental State Exam), measurement of vital signs, height and weight, BMI (calculated in database only), collection of demographics information, single 24-hour ambulatory SBP monitoring (daytime average SBP \geq 130 mmHg and <160 mmHg – qualifying criterion), and urine collection for a pregnancy test. If all study entry criteria are met, participants will be scheduled to return to the clinic for baseline assessments. In addition, the study participants will be asked to sign Medical Records Release Authorization if they qualify. This Authorization will be used exclusively to obtain medical records to acquire facts, details, and outcomes of Serious Adverse Events that occurred during the study and have to be reported to the sponsor and/or IRB.

6.4 Baseline Assessment and Randomization: If all study entry criteria are met, participants will be scheduled to return to the clinic for baseline assessments prior to randomization. Participants who have not yet had a physical evaluation or nursing assessment will complete this before undergoing physical tests. Participants will be asked to provide a fasting blood sample for evaluation of clinical safety lab values. We will also collect urine samples (first sample collected between 8 am to 11 am and another sample collected between 5 pm to 8 pm) at this visit, which will be slow frozen in a -80 freezer and analyzed after data collection is complete. The first sample will be collected when the participant comes in the morning to participate in the in-person visit. Then, the study coordinator will provide the urine sample collection cup for the participant to bring back home to collect the second urine sample. The study coordinators can help transport the second urine sample or, if the participant prefer, the participant could bring the urine sample back to the study coordinator. In addition, vital signs and weight

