will be measured, as well as exercise capacity with the 6-Minute Walk Test and self-assessed functionality with the Late Life Function and Disability Instrument (LLFDI). Participants will also be given the 24-h BP device to complete the 24-hour ambulatory recording and will have their arterial stiffness assessed. We will also collect adverse events and update medication changes. Finally, the study coordinator will provide participants with a supplement intake form to take home to record when the supplement is taken. Staff members will then discuss randomization procedures with participants. The participants will receive a return envelope/box to return the ambulatory BP device after the 24-hour recording.

6.5 Exercise Intervention: After random assignment to either the NREx or the PLEx groups, participants will engage in a three-days a week, center-based walking exercise intervention for 6 weeks. Following a brief warm-up, participants will be instructed to walk for 30 minutes at a 5-6 on the CR10 scale with encouragement for 10 minutes to be vigorous (7-8 on CR10 scale). Sessions will also include balance training to promote cool-down. Participants will be introduced to exercises in such a way that they begin with lighter intensity and gradually increase. The progressive nature of the intervention is designed to minimize discomfort and prevent injury. Blood pressure will be measured prior to each exercise session; the participant will not complete the session that day if he or she has an in-person SBP >200 mmHg or DBP >110 mmHg (AHA guidelines for exercise contraindication) measured at the exercise center.

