6.6. Supplementation: Participants will be randomly assigned to receive, in a double-blind fashion, either 1,000 mg/day of encapsulated NR (Niagen®) or placebo. The company ChromaDex (Irvine, CA) will provide both the NR and placebo capsules for the proposed study. Placebo capsules will be identical to those including NR. As noted above, a 6-week NR study of Martens et al. demonstrated that NR supplementation at a dose of 1,000 mg/day was safe in rather healthy middle-aged and older adults. Subjects will ingest NR (NIAGEN®; 500 mg, twice per day; ChromaDex, Inc.) or alike looking placebo capsules [10]. The participants will be provided with capsules sufficient for at least 3 weeks. The second 3-week portion of the capsules will be dispensed at 3-week follow-up visits by a study coordinator. A study coordinator will be given a jar with the study product by an unblinded staff person not-involved in this study. The not-involved staff member will be in possession of the identified randomization list and will provide this list after completing the enrollment and outcome measure analyses. The participants will receive a supplement intake diary to note the taken pills and a study coordinator will count the remaining pills at 3 and 6-week visits.

Data from the exercise interventions will be collected and stored in the study database. Following each session, participants will be asked to provide a rating of perceived exertion (RPE) for the session according to the Borg CR10 scale.

Table 1. Data collection summary by study visit.

Study phase	Pre-randomization		Randomization	
Visit description (FU=follow-up, CO=close-out)	Screen	Baseline	FU	CO
Visit number	1	2	3	4
Week number	-2	0	3 (+ or - 7 days)	6 (+ or - 7 days)
Informed consent, review of inclusion/exclusion criteria	X			
Medical history and medications, MSSE	X			
Height	X			
Weight	X	X	X	X
BMI (calculated in database only)	X			
Demographics information	X			
Physical Exam/nursing assessment	X*	X*		
Monitor vital signs	X	X	X	X
Ambulatory BP recording	X	X	X	X

CHAMPS Questionnaire	X			
Pregnancy test	X			
6 minute walk test		X		X
Late Life Function & Disability Instrument		X		X
Randomization		X		
Blood collection		X	X	X
Urine collection		X	X	X
Arterial stiffness		X		X
Dispense Supplement Intake Diary		X	X	
Dispense Study Supplement (NR or Placebo)		X	X	
Pill counts, collect diaries, assessment of adverse experiences			X	X
Collection of AEs and update medication changes		X	X	X

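### Ambulatory SBP is scheduled twice before treatment, but Section 10 uses only the baseline recording and names no SBP covariate, giving up precision on the primary outcome

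*Combined protocol and SAP*

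**What the plan says.** Section 6.3 lists "single 24-hour ambulatory SBP monitoring" among the screening procedures and gives its daytime average one purpose, eligibility (at least 130 and below 160 mmHg). In Table 1 the row "Ambulatory BP recording" is marked at screening (week -2), baseline (week 0), week 3 and week 6, with the first two visits under the pre-randomization heading.

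Section 6.4 states that "participants will be scheduled to return to the clinic for baseline assessments prior to randomization". The baseline recording is made at home after that visit: "The participants will receive a return envelope/box to return the ambulatory BP device after the 24-hour recording". Table 1 puts randomization and the first dispensing of supplement at the same visit.

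Section 10 sets the response: "Differences in outcome measures at the 3-week follow-up (or 6-week close-out) from baseline for each individual participant will be used as responses". The covariates are "two dummy variables representing the three treatment groups, age, and gender, and other baseline characteristics of participants will be used as covariates". Neither baseline nor screening SBP is named.

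**The concern.** One day's recording is a noisy measure of a person's usual daytime SBP. Under Section 10 the noise in the baseline recording passes in full into the change score. A second pre-treatment recording exists for every participant, and the analysis leaves it out.

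At stake is the precision of the NREx–PLEx contrast with about 15 completers per arm. Aim 1 also uses SBP change to project the size of a full trial, so the residual variance of the chosen analysis carries into that projection. Separately, a participant whose baseline recording fails has no change score and drops out of the SBP analysis, although a screening value exists. The documents give no failure rate, so this second loss cannot be sized.

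**Working it through.** **1. The plan's own figure.** Section 6.10 assumes "the mean decrease in SBP after a 6-week of intervention to be 20 mmHg, 10 mmHg and 15 mmHg in the three groups" (NREx, PLEx and NR in that order), SD of change 10, 15 per arm. NREx minus PLEx is 10 mmHg. The noncentrality is 10 / (10 × √(2/15)) = 2.74 on 28 df. Power is 84.8% one-sided at 0.05, which matches the stated 85%, and 75.3% two-sided. The plan states neither alpha nor sidedness. Two-sided 0.05 is used below.

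**2. Model.** Each recording = usual SBP (between-person SD b) + recording error (SD e). The follow-up value also carries individual response variation (SD r). The protocol's SD fixes 2e² + r² = 100. The documents give none of b, e or r. Assumed: b = 8, 12 or 15; (e, r) = (7.07, 0), (6.12, 5) or (5, 7.07); population mean 130 or 138. That makes 18 settings, each simulated with 800,000 candidates and restricted to screening SBP from 130 to below 160.

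**3. Residual variance with both recordings, by hand.** It is e² + r² + b²(e²/2)/(b² + e²/2). Selection on screening SBP does not change this, because screening SBP is in the model.
- b = 8, e = 7.07, r = 0: 50 + 64×25/89 = 68.0, SD 8.24, 32% below 100.
- b = 12, e = 6.12, r = 5: 62.5 + 144×18.75/162.75 = 79.1, SD 8.89, 21% below.
- b = 15, e = 5, r = 7.07: 75 + 225×12.5/237.5 = 86.8, SD 9.32, 13% below.

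Power at 15 per arm is about 89%, 84% and 81%.

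**4. The four analyses in the middle setting (mean 138, b = 12, e = 6.12), simulated with selection:**

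| Analysis | Residual SD | Two-sided power |
|---|---|---|
| Change from baseline, no SBP covariate | 9.99 | 75% |
| Change from baseline, two-recording mean as only SBP covariate | 9.71 | 78% |
| Baseline SBP as covariate | 9.30 | 81% |
| (a) follow-up SBP on the two-recording mean, or (b) change with both recordings as separate covariates | 8.88 | 84–85% |

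Against baseline adjustment alone, (a) or (b) saves 1 − 8.88²/9.30² = 9% of variance. Across the 18 settings the further saving is about 4–11%, or 2–4 power points. In this setting about 6 of the 9 points gained come from baseline adjustment alone.

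**5. Why the second row does poorly.** Write Y for follow-up, B for baseline and S for screening. Regressing Y − B on (S + B)/2 with slope β predicts Y with weight 1 + β/2 on B and β/2 on S. The weights must differ by exactly 1, whereas two equally noisy recordings deserve about equal weights. Across the 18 settings this model has 4–19% more residual variance than baseline adjustment alone, and only 2–15% less than the unadjusted score.

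**6. Cross-check with another model.** Assuming equal variances and an equal correlation of 0.5 to 0.9 between visits, again with selection, residual SD falls from 8.37 to 8.16 at the low end (1 − 8.16²/8.37² = 5%) and from 9.15 to 8.58 at the high end (12%). This agrees with the 4–11% in step 4.

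**7. Price of a covariate.** With 45 completers in three arms there are 42 within-arm df. Chance imbalance in one roughly normal covariate inflates the variance of a contrast by about 1 + 1/40 = 1.025 on average; two covariates give about 1 + 2/39 = 1.051. Steps 3 and 4 leave this out. Option (a) pays the same price as baseline adjustment, so its further 4–11% stands. Option (b) pays once more.

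**The case against.** The best case for leaving the plan alone is that nothing in it is wrong. The visit nearest treatment is a natural baseline, the screening value was selected on its size, and the study is a pilot whose own analysis section urges caution over hypothesis tests. Two to four power points beyond ordinary baseline adjustment is a refinement. It also rests on variances that the documents do not give. All of that stands, and it limits how hard the point can be pressed. It does not remove the point, because the data are already collected and the change is one sentence.

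Section 10 might also be said to cover baseline SBP already through its unspecified further covariates. It may. The list is open, so a reader cannot infer that SBP adjustment is excluded, nor that it is planned. Even if baseline SBP is included, the screening recording remains unused.

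Three stronger readings are tempting and fail:
- *Averaging the two recordings into the base of the change score.* Under equal correlation this cuts the change SD from 10 to 8.66. But screening SBP was selected at 130 mmHg or above. In the cross-check model its mean exceeded the baseline mean by 0 to 4 mmHg, so within-arm falls, which Section 6.10 also plans to estimate, would be inflated by 0 to 2 mmHg. Between-arm differences would not be biased.
- *Adding the two-recording mean to the model as written.* Step 5 shows that this is less precise than adjusting for baseline alone. It also rescues nobody with a failed baseline recording, since the response still needs that recording.
- *Taking both recordings as certainly untreated.* The baseline device goes home from the visit where randomization and dispensing are scheduled, so only the screening recording is assured to precede both.

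**Conclusion.** The point holds as a precision improvement worth making. Section 10 leaves out one of two scheduled pre-treatment recordings of the primary outcome and names no SBP covariate. Using both would cut residual variance by about 13–32% against the unadjusted change score and raise two-sided power from 75% to about 81–89%. The part that belongs to the screening recording itself is about 4–11% of the variance left after baseline adjustment.

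These figures rest on the protocol's SD of 10, a single follow-up time, 15 completers per arm, a two-sided 0.05 test, and assumed between-person and per-recording SDs. A reader might infer that the planned contrast is biased or the analysis invalid. The documents do not support that: the randomized comparison of change scores is unbiased, only less precise than it could be.

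**What to change.** In Section 10, for SBP only (arterial stiffness has no screening measurement), adopt one of these:

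- **(a)** The response is daytime SBP at weeks 3 and 6, with the mean of screening and baseline daytime SBP as a covariate, using whichever is available if one recording failed.
- **(b)** The response stays as change from baseline, with baseline SBP and screening SBP as two separate covariates.

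Option (a) costs one covariate and is the only one that keeps a participant whose baseline recording failed. Option (b) costs two. Under either, report within-arm changes from the baseline recording alone, and do not pair the change response with the two-recording mean as its only SBP covariate. Name the remaining covariates as well.

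Reconcile Section 6.4 with Table 1 so that the plan states that the baseline recording is complete before randomization and the first dose.

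The cost is one sentence in Section 10 and one on timing, with no new measurement. The downside is one or two degrees of freedom, the small inflation in step 7, and a gain whose size will be known only once the variances are seen.

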The objective of this study is to conduct a pilot study to refine and finalize elements critical to conducting a future, definitive randomized, controlled trial (RCT). We propose to recruit 54 persons aged ≥ 55 years with SBP ≥ 130 mmHg and < 160 mmHg for 6 weeks. Participants will be randomly assigned to receive either (1) 1,000 mg/day of NR plus 3 days/week of supervised, center-based walking exercise, or (2) the same exercise program combined with placebo, or (3) 1,000 mg/day of NR alone. Inclusion of all treatment groups will be important for detecting the potential benefit of NREx. High SBP will be determined at screening as daytime average above or equal 130 mmHg and below 160 mmHg, measured by the 24-hour BP device. All enrolled participants will undergo daytime continuous SBP measurements at baseline, 3 weeks, and 6 weeks, and arterial-stiffness measurements by pulse-wave velocity (PWV) at baseline and 6 weeks. This study will enable us to address the following aims, all of which are of critical importance for designing a full-scale trial.

Aim 1. To obtain critical data necessary to project the sample size needed for a full-scale trial using the change in SBP, as the primary outcome and;

Aim 2. Using the change in arterial stiffness, as the secondary outcome.

6. Research Plan:

We propose to conduct a randomized, controlled pilot trial to test if nicotinamide riboside improves an effect of aerobic exercise training on cardiovascular function among hypertensive older adults. Following study entry, participants (N = 54) will be randomly assigned to either NREx, NR or PLEx groups for 6 weeks. Exercise groups will be involved in three center-based walking training sessions per week. We anticipate that up to an additional 20 individuals enrolled may discontinue participation in the project prior to completion, and that we may have to screen up to 250 additional individuals to reach our recruitment goal of 54 subjects.

6.1 Participants: Eligible participants will be males or females ≥ 55 years of age with daytime average SBP ≥ 130 mmHg and < 160 mmHg.

Table 3.1.1. Inclusion and exclusion criteria.

Inclusion Criteria

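### Section 10 permits but does not require each outcome's own baseline value as a covariate in the change-score model. Leaving it out adds no bias but can cost precision, and the SBP baseline recording is not pinned down

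*Combined protocol and SAP*

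**What the plan says.** Section 10 takes as responses "Differences in outcome measures at the 3-week follow-up (or 6-week close-out) from baseline", and states that "two dummy variables representing the three treatment groups, age, and gender, and other baseline characteristics of participants will be used as covariates". The further characteristics are not listed. The same model is applied to every outcome. Section 10 also warns that "The relatively small sample size may imbalance pre-randomization covariates", and its only stated response is caution when interpreting tests.

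Section 5 (Specific Aims) shows that the data exist: participants have "daytime continuous SBP measurements at baseline, 3 weeks, and 6 weeks, and arterial-stiffness measurements by pulse-wave velocity (PWV) at baseline" and again at 6 weeks.

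On timing, section 6.4 says "participants will be scheduled to return to the clinic for baseline assessments prior to randomization". It then continues: "Participants will also be given the 24-h BP device to complete the 24-hour ambulatory recording", with an envelope or box supplied "to return the ambulatory BP device after the 24-hour recording". Table 1 marks randomisation and the first dispensing of supplement at that same baseline visit. Section 6.3 provides one other recording before randomisation, the "single 24-hour ambulatory SBP monitoring" used to qualify participants at screening.

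**The concern.** A change score looks as if it already adjusts for baseline, but it only fixes the slope of follow-up on baseline at 1. When the true slope differs, any chance difference between arms at baseline carries into the estimated contrast. Fitting baseline as a covariate removes that component. Age and gender are named in Section 10, while the covariate most directly tied to the response is left to the analyst. Two analysts could both follow the section faithfully and report different primary estimates.

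What is at stake is the width of the interval for NREx versus PLEx, and how exposed the estimate is to the small-sample imbalance that Section 10 itself expects.

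A second matter affects the change score and the covariate alike. If the 24-hour baseline recording is worn home from the visit at which randomisation and dispensing take place, it may run past randomisation or the first dose. The plan does not say which recording counts as the SBP baseline.

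**Working it through.** **Inputs from section 6.10.** Mean SBP decreases of 20 (NREx) and 10 (PLEx) give a difference of 10 mmHg. The SD of the change is 10 and there are 15 evaluable participants per arm. Stated power is 85%.

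**Inputs assumed.** The documents do not give r (correlation of baseline with follow-up) or k (follow-up SD divided by baseline SD). I take r = 0.3, 0.5, 0.7, 0.9 and k = 1 or 1.2. The entry range of 130 to below 160 mmHg could compress baseline spread and push k above 1.

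**The plan's own figure.** SE of the contrast = 10 × √(2/15) = 3.65 mmHg. Noncentral t power with 28 df is 84.8% at one-sided 0.05 and 75.3% at two-sided 0.05. The stated 85% is therefore matched by a one-sided 0.05 test; section 6.10 gives neither alpha nor sidedness. It uses the unadjusted change SD, so it takes no credit for baseline adjustment.

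**Variance with and without baseline, one follow-up.** Let s0 be the baseline SD.
- Change score: s0²(1 + k² − 2rk)
- Adjusted for baseline: s0²k²(1 − r²)
- Large-sample reduction: (1 − rk)² / (1 + k² − 2rk)

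Example, r = 0.5: k = 1 gives 0.25/1.00 = 25.0%; k = 1.2 gives 0.16/1.24 = 12.9%.

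**Cost of estimating the slope.** Given the baselines, the adjusted contrast has variance σ²[2/15 + (baseline difference)²/SSx], where SSx is pooled within three arms (42 df). For a normal baseline the average is σ²(2/15)[1 + 1/(42 − 2)], so the variance ratio is multiplied by 1.025.

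Holding the change SD at 10 implies s0 = 10/√(1 + k² − 2rk). Half-width is t(0.975) × SE, with 42 df unadjusted (2.018 × 3.65 = 7.37 mmHg) and 41 df adjusted.

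| k | r | Large-sample cut | Ratio × 1.025 | Net cut | 95% half-width (mmHg) | Implied baseline SD |
|---|---|---|---|---|---|---|
| 1 | 0.3 | 35.0% | 0.666 | 33% | 6.02 | 8.5 |
| 1 | 0.5 | 25.0% | 0.769 | 23% | 6.47 | 10.0 |
| 1 | 0.7 | 15.0% | 0.871 | 13% | 6.88 | 12.9 |
| 1 | 0.9 | 5.0% | 0.974 | 3% | 7.28 | 22.4 |
| 1.2 | 0.3 | 23.8% | 0.781 | 22% | 6.52 | 7.6 |
| 1.2 | 0.5 | 12.9% | 0.893 | 11% | 6.97 | 9.0 |
| 1.2 | 0.7 | 3.4% | 0.990 | 1% | 7.34 | 11.5 |
| 1.2 | 0.9 | 2.3% | 1.002 | 0% | 7.38 | 18.9 |

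Simulation of three arms of 15 gives ratios of 0.67/0.77/0.87/0.97 (k = 1) and 0.78/0.90/0.99/1.00 (k = 1.2), in agreement. The percentage cuts have no units, so under the same r and k they apply to cfPWV, which has a single follow-up.

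**Bias.** In simulation with complete data at r = 0.5, k = 1 and a true difference of −10 mmHg, mean estimates were −10.02 without baseline and −10.01 with it.

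**Imbalance.** At r = 0.5, k = 1 (baseline SD 10), a one-SD chance difference between two arms is 10 × √(2/15) = 3.65 mmHg. It moves the unadjusted estimate by (1 − 0.5) × 3.65 = 1.83 mmHg relative to the adjusted one. This shift is the same thing as the lost precision, seen in a single trial.

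**Timing.** Section 6.4 places baseline assessments before randomisation. The same section has the recording completed after the participant leaves, and Table 1 puts randomisation and dispensing at the visit being left. The text does not show how all three can hold for the ambulatory recording.

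**The case against.** The strongest reply is that nothing has been omitted. Baseline SBP and cfPWV are baseline characteristics, so the open phrase in Section 10 already covers them. That stands as far as it goes: a reader might infer that the plan leaves baseline out, and the documents do not support that. What they support is that inclusion is optional.

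The second reply is that the gain is uncertain and can vanish. This also stands. At k = 1.2 it is about 1% at r = 0.7 and nil at r = 0.9, once the slope is estimated from the trial's own data. The r = 0.9 rows need a baseline SD of about 19 to 22 mmHg, which sits poorly with an entry range 30 mmHg wide, so they are the least plausible. Age, gender and other covariates could also absorb part of the gain.

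The third reply is that this is a pilot meant to give variance estimates and descriptive effects. That limits the weight of the point, but it does not justify leaving the choice open when the data are already collected.

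The recording question is separate from covariate choice, since it affects the change score either way. The statement in section 6.4 that baseline comes first is a partial answer, but it does not dispose of a recording finished after the visit.

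**Conclusion.** The point holds as a gap in commitment. Section 10 allows the outcome's own baseline as a covariate but does not require it. If baseline is left out, the variance of the NREx versus PLEx contrast is higher than it need be under most of the assumed values. With equal SDs, adjustment would remove about 33% at r = 0.3, falling to 3% at r = 0.9. With k = 1.2 it would remove about 22%, falling to nothing. These figures rest on the change SD of 10 and 15 per arm from section 6.10, one follow-up, complete data, and assumed r and k.

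Two stronger readings are tempting and unsupported. A reader might infer that the treatment contrast is biased; over randomisation with complete data it is not. A reader might also infer that the 85% power is overstated because baseline is missing; that figure already rests on the unadjusted change SD.

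This is a worthwhile precision improvement in a pilot. It does not invalidate the analysis. The timing of the SBP baseline recording is a real inconsistency that needs resolving whichever model is used.

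**What to change.** Add to Section 10: each model includes the baseline value of the same outcome (daytime SBP for SBP, cfPWV for cfPWV) as a fixed covariate alongside arm, age and gender, and any further baseline covariates are listed before unblinding. The change without baseline adjustment can be reported as supportive. The cost is SAP wording and one degree of freedom per model, with no new data.

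Separately, reconcile section 6.4 with Table 1 and state which ambulatory recording is the pre-randomisation SBP baseline, for the change score and the covariate alike. If the recording used is not complete before randomisation and the first dose, say so. The screening recording is another pre-randomisation value, but its range is restricted by the entry criterion. This step may need the visit sequence clarified in the protocol as well as a sentence in the SAP.
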